15.1.3 Adverse Events Leading to Discontinuation of Study Intervention

Since the study intervention is administered as single dose treatment on Day 1, discontinuation of study intervention due to AEs or any other reason cannot happen.

15.2 Deaths, Other Serious Adverse Events, and Other Significant Adverse Events

15.2.1 Deaths

Death date and reason for death are collected on the “DEATH” CRF form. A participant data listing including date and reason of death, PT of AEs with fatal outcome together with selected dosing information (date of administration) will be provided

15.2.2 Serious Adverse Events

The following frequency tables will be prepared for serious TEAEs:

- Incidence of serious TEAEs by SOC and PT
- Incidence of related serious TEAEs by SOC and PT

A listing of SAEs will also be provided with the relevant information.

15.2.3 Other Significant Adverse Events

AEs of special interest (AESIs) include the following events as defined by the CTP:

- Liver events, monitored through LFTs that will include ATS, ALT, and AST, as well as TB and ALP
- Neurological events, monitored through specific neurological clinical examinations

AESIs will be identified by the corresponding flag on the AE page of the eCRF and by specifically search for them with an appropriate list of PTs. A frequency table of AESIs by SOC and PT will be provided.

15.2.4 Disease Related Events

Disease related events are captured separately in the same manner as Adverse Events. They will be separated by the time of their occurrence, i.e. events with onset or worsening dates on or after the first administration of study intervention and events with onset or worsening dates before the first administration of study intervention. Frequency tables displaying incidences of disease related events will be provided by SOC and PT separately for events occurring before and after study intervention as defined above.

15.2.5 Clinical Laboratory Evaluation

The following laboratory parameters will be measured during the trial and reported as part of the safety evaluation (for a detailed list of parameters refer to Appendix 10 of the CTP):

- Hematology
- Biochemistry

Summary tables over time displaying absolute values and changes from Baseline will be provided. For a graphical presentation line plots of lab parameters standardized to times ULN over time will be provided for each participant. Thereby, plots should be grouped by participants of different cohorts and by lab parameters in the following way:

- Biochemistry:

- Alanine Aminotransferase, Alkaline Phosphatase, Aspartate Aminotransferase, Bilirubin
- Calcium, Creatinine, Glucose, Chloride
- Potassium, Protein, Sodium
- Hematology:
 - Basophils, Eosinophils
 - Hematocrit, Hemoglobin
 - Leukocytes, Lymphocytes, Monocytes, Neutrophils, Platelets, Reticulocytes

In addition, shift tables from Baseline based on normal ranges will be given.

In order to investigate possible events of Hy's Law, an eDISH Plot will be provided

Outputs will be presented using the Merck Standard Unit Catalogue (see Appendix 2). Normal ranges will be provided by the local laboratories, and out of range flags will be calculated based on the normal ranges. Laboratory data not transferred in standard units will be converted to before processing. Both original units and standard units will be provided in the SDTM domain.

Subject Data Listings will only be provided for subjects with abnormal test results (lower than LLN and higher than ULN, abnormal CS and abnormal NCS).

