Adaptive Aspects of Study Design	
Safety stopping criteria:
 
If one of the criteria is met, the current study will be put on hold until it has been established that the benefit-risk of the combination is optimal
 
1. Liver toxicity signals: > 1 participant present any of the following criteria:
a. Presence of Hy's law criteria (ALT and/or AST > 3 × ULN, and elevation of serum TB to > 2 × ULN, without initial findings of cholestasis [elevated serum ALP], with no other reason to explain the combination of increased transaminases and TB).b. CTCAE v5.0 ≥ Grade 3 ALT or AST increases, that do not return to normality or below 1.5 × the ULN at the end of follow-up (28 days after first treatment).c. CTCAE v5.0 ≥ Grade 3 ALT or AST increases accompanied by posttreatment established coagulation disorder at any time (INR ≥ 1.5) not related to another underlying condition.2. CNS signals:
a. if ≥ 1 participant present persistent severe study intervention-related CNS disorders considered AEs that do not resolve within 2 weeks after the onset, orb. if ≥ 2 participants present persistent severe study intervention-related CNS AEs irrespectively of the recovery status, orc. if ≥ 1 participants experience a serious study intervention-related CNS AE.3. SUSAR Grade 4 or higher according to the CTCAE v5.0.
----------------------------------	---

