Diagnostic Assessments	
12. Serum creatinine levels $\geq 2 \times$ ULN.
 
13. AST and/or ALT $> 1.5 \times$ ULN, regardless of the level of TB.
 
14. AST/ALT > 1.0 and $\leq 1.5 \times$ ULN and TB is $> 1.5 \times$ ULN.
 
15. TB $> 2 \times$ ULN, regardless of the level of AST/ALT.
 
16. A marked Baseline prolongation of QTc interval > 450 msec applying the Fridericia's correction.
 
17. Known disturbances of electrolyte balance, \geq Grade 2 according to the CTCAE v5.0, e.g. hypokalemia, hypocalcemia, or hypomagnesemia.
 
18. Moderate to severe anemia (hemoglobin level < 8 g/dL).
 
19. Severe malnutrition as reflected by a mid-upper arm circumference < 18 cm for adolescents (Hadush 2021) or defined as a BMI < 18.5 kg/m² for adults.
 
20. Severe vomiting, defined as > 3 times in the 24 hours prior to enrollment in the study or inability to tolerate oral treatment, or severe diarrhea defined as ≥ 3 watery stools per day.

Other Exclusions	
21. Known history of hypersensitivity, allergic or adverse reactions to pyronaridine or M5717; contraindications to atovaquone and/or proguanil (Malarone SmPC).

Category	Criterion
	22. Known history or current substance abuse.

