8.2.4 Clinical Safety Laboratory Tests

Blood and urine samples will be collected for the clinical laboratory tests listed in [Appendix 10](#) at the timepoints listed in the SoA. All samples will be clearly identified.

Additional tests may be performed at any time during the study, as determined necessary by the Investigator or required by local regulations

The tests will be performed by a local laboratory.

The Sponsor must receive a list of the local laboratory normal ranges before shipment of study intervention(s). Any changes to the ranges during the study must be forwarded to the Sponsor.

The Investigator will review each laboratory report, document this review, and record any clinically significant changes occurring during the study as an AE, unless it does **not** meet the AE definition, as specified in [Appendix 5](#). The laboratory reports will be filed with the source documents.

Pregnancy testing (serum or highly sensitive urine) will be conducted as indicated in the SoA (see Section 1.3).

Additional serum or urine pregnancy testing may be conducted at any time during the study to establish the absence of pregnancy, at the Investigator's discretion or if local regulations require them.

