9.7 Definition of Baseline and Change from Baseline

Baseline is defined as the last non-missing measurement (including those collected at an unscheduled visit) prior to the first dose of IMP. If an assessment that is planned to be performed before study intervention per protocol is performed on the same day as the start of study

intervention, respectively, but the assessment time is not available, it will be assumed that it was performed prior and will be considered as baseline.

Change from baseline (CFB) and percent CFB any post-baseline visit will be computed as follows:

- $CFB = \text{visit value} - \text{baseline value}$
- $\%CFB = 100 * (\text{visit value} - \text{baseline value}) / \text{baseline value}$

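### Laboratory shift tables by normal range only: a liver enzyme rise from 1.4 to 10 x ULN is tabulated as high-to-high, and no table counts severity by cohort from the laboratory values

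*SAP*

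**What the plan says.** SAP 15.2.5 plans five kinds of laboratory output: summary tables of values and changes from baseline, line plots for each participant, shift tables, an eDISH plot, and listings for participants with abnormal results.

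- **Shift tables.** "In addition, shift tables from Baseline based on normal ranges will be given". The section gives no other category and no post-baseline time point (worst value or by visit). Flags follow the same basis: "out of range flags will be calculated based on the normal ranges".
- **Line plots.** "line plots of lab parameters standardized to times ULN over time will be provided for each participant".
- **Baseline (SAP 9.7).** "Baseline is defined as the last non-missing measurement" before the first dose.
- **Values used (SAP 9.3).** Repeat and unscheduled measurements are listed but kept out of analyses and summaries, except repeats made for technical reasons. SAP 9.4 also labels visits outside their window as unscheduled, subject to data review.
- **Grading.** CTCAE v5.0 is applied to adverse events (SAP 15.1), and the worst-grade tables count TEAEs (SAP 15.1.1).
- **Tier 1 (SAP 15.1.2).** One item draws on laboratory data: an AST/ALT ratio outside 0.7 to 1.4.

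The protocol works with finer liver categories. Exclusion 13 is ALT or AST > 1.5 x "ULN, regardless of the level of TB". Exclusion 14 adds those above 1.0 and up to 1.5 x ULN if TB is > 1.5 x ULN. The Schedule of Activities and Appendix 6 act on > 3 x ULN for the enzymes and > 2 x ULN for TB. Stopping criteria 1b and 1c in Protocol 4.1 refer to "Grade 3 ALT or AST increases, that do not return to normality" and "Grade 3 ALT or AST increases accompanied by posttreatment established coagulation disorder".

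**The concern.** Liver events are adverse events of special interest, and chemistry is measured at every visit. A three-category shift table (low, normal, high) separates participants only at the limits of normal. The protocol's own liver thresholds all lie well above the upper limit, inside the single high category. The table therefore cannot tell a cohort with several marginal values from a cohort with several severe ones, and it records no change for anyone who enters slightly high.

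As the SAP stands, graded liver counts come only through adverse event reporting. Under Protocol 8.2.4 the investigator will "record any clinically significant changes occurring during the study as an AE". Appendix 5 allows abnormal results attributed to the underlying disease to be left out, and treatment is open label. At stake is whether the final report contains a cohort-by-cohort severity count that does not depend on that judgement.

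**Working it through.** The plan gives no figure to reproduce, so the check traces possible values through the planned categories.

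**1. Can a participant enter above ULN?** Exclusions 13 to 15, applied to ALT 1.4 x ULN:

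| TB at entry (x ULN) | Eligible on liver criteria? |
|---|---|
| 1.0 | yes |
| 1.5 | yes |
| 1.6 | no (exclusion 14) |

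Yes, if TB is not above 1.5 x ULN. Under SAP 9.7 that value is the baseline, and it is categorised as high.

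**2. What does the shift table record?** Values are multiples of ULN; high means > 1.0.

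| Baseline | Post-baseline | Ratio | > 3 x ULN? | Cell |
|---|---|---|---|---|
| 0.9 | 1.01 | 1.12 | no | normal-to-high |
| 0.9 | 10 | 11.11 | yes | normal-to-high |
| 1.1 | 1.2 | 1.09 | no | high-to-high |
| 1.4 | 3.1 | 2.21 | yes | high-to-high |
| 1.4 | 10 | 10/1.4 = 7.14 | yes | high-to-high |

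Two cells hold all five cases, and each mixes marginal rises with rises beyond the protocol's 3 x ULN threshold.

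**3. Does another table give a severity count from laboratory values?**

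- *Descriptive summaries.* SAP 9.3 includes the minimum and maximum, so 10 x ULN at a scheduled visit shows as the cohort maximum. That identifies one extreme and not how many participants exceeded a threshold. The mean hardly moves: with 192/4 = 48 randomised per cohort, one rise from 1.4 to 10 x ULN shifts it by (10 - 1.4)/48 = 0.18 x ULN.
- *Tier 1 ratio.* If AST and ALT are both multiplied by k, then (k x AST)/(k x ALT) = AST/ALT. AST 400 and ALT 400 U/L give 1.0, which counts as normal. A rise in ALT alone of 7.14-fold takes a starting ratio of 0.7 to 1.4 down to about 0.10 to 0.20 and is counted as abnormal, but with no indication of severity.
- *eDISH, line plots, listings.* These show individual values and provide no cohort counts.
- *TEAE worst-grade tables.* These count by severity, but only for rises reported as adverse events.

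**4. Which values reach the tables?** Appendix 6 asks for repeat testing within 48 to 72 hours of ALT or AST > 3 x ULN. From Day 8 scheduled visits are weekly, so such repeats will usually fall between them and count as unscheduled. If the peak occurs on a repeat, SAP 9.3 keeps it out of the summaries. It will be in the listings; the SAP does not say whether the plots use it.

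**5. Comparison within the SAP.** Vital signs have banded maximum changes (SAP 15.3), and QT/QTcF has counts above 450, 480 and 500 ms (SAP 15.4.1). The liver laboratory values have no equivalent.

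**The case against.** The strongest reply is that the size of any rise is already well covered. The summaries give a cohort maximum, the line plots are in multiples of ULN and grouped by cohort, the eDISH plot is the planned display for possible Hy's law cases, and out-of-range values are listed. Transaminase and bilirubin increases are named events of special interest, reportable within 24 hours. The SAP finds them by eCRF flag and by preferred-term search, and analyses ALT and AST increased as Tier 1 events against Cohort 4. The study is exploratory and descriptive, with 45 evaluable participants per cohort planned, so individual displays can be read in full.

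Most of this stands, and it rules out several stronger readings that a reader might infer:

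- *That a severe rise would go unseen, or that cohorts cannot be compared on severity.* The outputs above show magnitude by cohort; only the count by severity threshold is absent.
- *That the stopping rule cannot be operated.* It applies during conduct, and SAP 9.6 places any ad hoc DMC analysis under a separate plan that is not among these documents. Nor would a grade table reproduce criteria 1a to 1c: 1a also needs ALP and the exclusion of other causes, 1b needs non-recovery at 28 days, and 1c needs INR, which is not in the Appendix 10 panel.
- *That the shift table is the only categorical laboratory analysis.* The Tier 1 ratio is another.
- *That plots scaled to ULN conceal low-side harm.* Dividing by ULN only rescales the axis; scaling to LLN is a presentation preference.

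The reply does not supply a severity count that is independent of adverse event reporting, and it does not deal with peaks seen only at repeat visits.

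**Conclusion.** The point holds as a gap in final reporting. Under SAP 15.2.5 any rise from a baseline above 1.0 and up to 1.5 x ULN counts as no shift, and for a normal baseline every value above ULN shares one cell. No planned table gives the number of participants per cohort who cross the protocol's own liver thresholds, as measured in the laboratory.

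The conclusion rests on reading a normal-range shift as low, normal and high, which the LLN and ULN flags support; the SAP names no other category. The 1.4 x ULN example also needs TB not above 1.5 x ULN. The documents do not say how many participants will enter above ULN, so the number affected is unknown; the loss of size among participants with a normal baseline does not depend on it. The documents do not reproduce the numeric CTCAE limits, so no grade is assigned here to 10 x ULN. The gap is moderate in weight: information on severity exists, but not as a count, and peaks at unscheduled repeats drop out of the summaries.

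**What to change.** In SAP 15.2.5, keep the normal-range shift tables and add:

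1. Shift tables from baseline grade to worst post-baseline grade by CTCAE v5.0, calculated from the laboratory values for each graded parameter. State how a participant with an abnormal baseline is graded.
2. Cohort counts and percentages of participants with, at any time after baseline, ALT or AST > 3 x ULN, TB > 2 x ULN, both together, and Grade 3 or higher ALT or AST. These thresholds are already in the protocol.
3. A sentence that both outputs include unscheduled and repeat values, as an exception to SAP 9.3, and that says whether the line plots and eDISH plot do so.

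The cost is SAP wording and a few more standard tables to program. No new data, visits or grading scale are needed.

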12-lead ECG		X ^c							Will include QTcF assessment as scheduled and as clinically indicated. All ECGs will be recorded in triplicate. ^c ECG assessments will be performed at Day 1/Visit 1 prior to dosing and 2 hours postdose.	
Vital signs		X ^d	X	X	X	X	X	X	Will include supine blood pressure and pulse rate. Vital sign measurements will be taken after the participant has been supine for \geq 5 minutes. Taken at screening and at predose and at the timepoints listed. ^d Measurements on Day 1/Visit 1 will be taken predose, and 2 and 4 hours postdose, if applicable.	

Assessments & Procedures	Outpatient	Outpatient/Inpatient ^a		Outpatient					Notes	
Visit Number	Prescreening	Scr + Visit 1 ^a	Visit 2 ^a	Visit 3	Visit 4	Visits 5 to 12	Visit 13	Unscheduled Visit	
^a Visit 1 and 2: Participants randomized to Cohorts 1 to 3 will remain in hospital or stay in the vicinity of the sites for 24 hours for PK sampling and assessment of parasitemia (see Table 2).
 
Participants randomized to Cohort 4, will visit the clinic on Days 1, 2, and 3 for dosing in an outpatient setting
	
Timepoint	Prescreening	Day 1	Day 2	Day 3	Day 4	Week 2 to 9 (weekly visits starting at Day 8)	EOS (last visit) Week 10, Day 64 ^b	Can be required due to AEs, and AESIs; follow-up of AEs and AESIs	
^b Day 64 or day of completion or premature discontinuation.
 
Participants will remain in the study until parasitemia or until Day 64, whichever comes first.
 
All EOS evaluations will be completed before providing antimalarial rescue treatment if required.
	
Hematology, chemistry, and urinalysis		X ^e	X	X	X	X	X	X	
Hematology, biochemistry, urinalysis as scheduled and when clinically indicated.
 
A sample should be collected before rescue treatment administration if required.
 
^e If abnormalities are detected on Day 1 a follow-up sample will be taken on Day 2.
 
If increase in ALT > 3 x ULN and/or TB > 2 x ULN, a follow-up is required including ALT, AST, ALP, and TB.
 
Timing of the follow-up visits until resolution will be at the discretion of the Investigator.
	

Assessments & Procedures	Outpatient	Outpatient/Inpatient ^a		Outpatient					Notes	

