Appendix 6 Liver Safety: Suggested Actions and Follow-up Assessments

The DILI will be defined as follows:

- An elevated ALT or AST $> 3 \times$ ULN. Often with ATs much greater: 5 to $10 \times$ ULN.
- An elevated ALT or AST $> 3 \times$ ULN plus serum TB $> 2 \times$ ULN, without findings of cholestasis (defined as serum ALP activity $< 2 \times$ ULN).
- No other reason can be found to explain the combination of increased AT and serum TB, such as viral hepatitis, alcohol abuse, ischemia, preexisting liver disease, or another drug capable of causing the observed injury.

An increase of serum ALT or AST to $> 3 \times$ ULN should be followed by repeat testing within 48 to 72 hours of all 4 of the usual serum measures (ALT, AST, ALP, and TB) to confirm the abnormalities and to determine if they are increasing or decreasing. The need for prompt repeat testing is especially great if AT is much $> 3 \times$ ULN and/or TB is $> 2 \times$ ULN.

If symptoms persist or repeat testing shows AT $> 3 \times$ ULN for participants with normal Baseline measures, it is appropriate to initiate close observation to determine whether the abnormalities are improving or worsening.

Close observation includes:

- Repeating liver enzyme and serum bilirubin tests 2 or 3 times weekly. Frequency of retesting can decrease to once a week or less if abnormalities stabilize and the participant is asymptomatic.
- Obtaining a more detailed history of symptoms and prior or concurrent diseases.
- Obtaining a history of concomitant drug use (including nonprescription medications and herbal and dietary supplement preparations), alcohol use, recreational drug use, and special diets.
- Ruling out acute viral hepatitis types A, B, C, D, and E; autoimmune hepatitis; NASH; hypoxic/ischemic hepatopathy; and biliary tract disease.
- Obtaining a history of exposure to environmental chemical agents.
- Obtaining additional tests to evaluate liver function, as appropriate (e.g. INR, direct bilirubin).
- Considering gastroenterology or hepatology consultations.

All study participants showing possible DILI should be followed until all abnormalities return to normal or to the Baseline state.

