9.3 Presentation of Tables/Figures/Listings

Tables and figures will be presented by the different treatment groups as denoted within the previous paragraph. Individual participant data listings will be provided. All listings will be sorted by treatment group (starting with the lowest M5717 dose and ending with the natural infection cohort), subject ID and scheduled time point.

Repeated and unscheduled measurements included in the listings will not be used for statistical analyses or summaries, unless the repeated measurement was performed due to unreliable values/technical reasons, e.g., clotted samples. They will be flagged as such in the listings.

Presentation of continuous and qualitative variables

Unless otherwise specified, continuous variables will be summarized using descriptive statistics, i.e. the number of participants with non-missing values (n), the number of participants with missing values, (nmiss), mean, standard deviation, median, 25th percentile (Q1) and 75th percentile (Q3), minimum, and maximum.

Qualitative variables will be summarized by frequency counts and percentages. Unless otherwise stated the calculation of proportions will be based on the number of participants of the analysis set of interest. Therefore, counts of missing observations will be included in the denominator and presented as a separate category.

Descriptive statistics by nominal visit or time point, e.g., for laboratory measurements, will include only data from scheduled visits.

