9.4 Analysis visit windows

For weekly visits (Visit 5 to Visit 12) and for the EOS visit (Visit 13) a visit window of ± 1 and ± 2 days are defined in the CTP. Visit windows for the visits on days 1 and 2 can be taken from Table 2 of the CTP in Section 1.3.

In case any visit occurred outside of the defined visit windows it will be allocated to “unscheduled”. In case too many measurements are observed outside of the defined visit windows, it will be decided on an individual basis whether those can be allocated to scheduled visits in a reasonable manner during data review before database lock.

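### Read as written, SAP 9.3 keeps DILI-triggered liver retests out of the eDISH plot and the other laboratory-based liver displays, and SAP 15.2.5 makes no exception

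*SAP*

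**What the plan says.** **Outputs.** SAP 15.2.5 plans by-visit laboratory summaries, per-participant line plots in multiples of ULN, shift tables from baseline on normal ranges, and, for Hy's Law, "an eDISH Plot will be provided". It defines neither the input records for the plot nor a peak ALT, AST or bilirubin.

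**General data rule.** SAP 9.3, whose heading covers tables, figures and listings, states: "Repeated and unscheduled measurements included in the listings will not be used for statistical analyses or summaries". The only exception is "unless the repeated measurement was performed due to unreliable values/technical reasons, e.g., clotted samples". A further sentence limits by-visit descriptive statistics: "e.g., for laboratory measurements, will include only data from scheduled visits".

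**Windows.** SAP 9.4 notes that for the weekly and end-of-study (EOS) visits "a visit window of ± 1 and ± 2 days are defined in the CTP". Anything outside a window becomes unscheduled. Case-by-case reallocation is foreseen only if too many measurements are affected.

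**Retests.** Under Protocol Appendix 6, ALT or AST above 3 x ULN is followed by repeat ALT, AST, ALP and total bilirubin within 48 to 72 hours. If symptoms persist or the repeat confirms the rise, close observation includes "Repeating liver enzyme and serum bilirubin tests 2 or 3 times weekly", which may later drop to weekly or less. Protocol Section 1.3, Table 1 adds: "Timing of the follow-up visits until resolution will be at the discretion of the Investigator". The same table has an unscheduled-visit column that includes chemistry.

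**The concern.** Scheduled-only data suit a table by nominal visit. They do not suit a display meant to show each participant's worst values. Hy's Law is a joint criterion on aminotransferase and bilirubin, and bilirubin may cross its threshold after the aminotransferase value that prompted the retest. If retests are excluded, the extra samples taken to follow a suspected case are the ones the display ignores.

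Liver events are one of the two AESI categories (Protocol 8.3.6), and Hy's Law criteria are among the study-hold criteria (Protocol 4.1). With about 45 evaluable participants per cohort, one participant placed in the wrong quadrant changes how the plot reads. The AESI and Tier 1 tables count preferred terms and do not pair aminotransferase with bilirubin within a participant. The planned displays that do are the eDISH plot and the line plot that groups the liver tests.

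**Working it through.** The plan gives no figure to reproduce. The check traces the rule to the outputs, then compares the retest timing with the visit windows.

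**1. Does the technical exception cover these retests?** No. It concerns unreliable values such as clotted samples. An Appendix 6 retest is taken because the first value may be real.

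**2. Does the SAP say so when it wants unscheduled values?** Yes, in two places. SAP 9.7 expressly allows unscheduled measurements for baseline. SAP 15.4.1 gives all collected ECG values for participants with notable findings. SAP 15.2.5 has no such statement for the eDISH plot, line plots or shift tables.

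**3. Can a retest fall in a scheduled window?** Inputs:
- Visits on Days 1, 2, 3 and 4.
- Weekly visits on Days 8, 15, ..., 57, each with a ±1 day window.
- EOS on Day 64, ±2 days (Days 62 to 66).
- Retest 2 or 3 days after the triggering visit (48 to 72 hours).

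For a weekly visit planned on day d:
- Latest visit day: d + 1. Latest retest: d + 1 + 3 = d + 4.
- Next weekly window opens at d + 7 − 1 = d + 6.
- For d = 57, the EOS window opens on Day 64 − 2 = 62, while the latest retest is Day 61.

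The retest always comes before the next window. By enumeration: 8 weekly visits x 3 possible visit days x 2 retest delays = 48 combinations, of which 0 fall in the next scheduled window. For example, a visit on Day 8 gives a retest on Day 10 or 11, and the next window is Days 14 to 16. A visit one day early with a 2-day retest lands in its own window (visit Day 7, retest Day 9), but that value is still a repeat.

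| Trigger day | 2-day retest | 3-day retest |
|---|---|---|
| 1 | Day 3, scheduled | Day 4, scheduled |
| 2 | Day 4, scheduled | Day 5, none |
| 3 | Day 5, none | Day 6, none |
| 4 | Day 6, none | Day 7, in Day 8 window |
| 64 | Day 66, in EOS window but a repeat | Day 67, none |

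So some retests from Days 1 to 4 can coincide with a scheduled visit. From Day 8 they do not.

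**4. Close observation.** With 2 or 3 tests a week and one scheduled visit a week, at least 2 − 1 = 1 or 3 − 1 = 2 tests per week are repeat or unscheduled.

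**5. Early EOS.** Participants leave the schedule at parasitemia (Protocol Table 1). Liver tests after that have no scheduled visit to match.

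**6. What the display would miss.** Suppose ALT is above 3 x ULN with bilirubin below 2 x ULN on Day 15, bilirubin is above 2 x ULN at the Day 17 or 18 retest, and it is back below by Day 22. On scheduled values alone this participant is not in the Hy's Law quadrant. The triggering ALT stays in the plot; the bilirubin crossing does not.

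**7. Shift tables.** They use normal ranges. An ALT or AST above 3 x ULN is already above range, so a higher retest does not change its category. The main exception is a bilirubin that first leaves the normal range at a retest.

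**The case against.** **SAP 9.3 does not name the eDISH plot or the individual line plots.** Both show individual participants and are not plainly statistical analyses or summaries. The separate sentence on by-visit laboratory statistics would also be largely redundant if every laboratory output were already scheduled-only. This stands in part: a programmer could reasonably use all values. But the section covers figures, repeat and unscheduled values are given a place only in listings, and 15.2.5 gives no exemption. Two programmers could therefore produce different Hy's Law plots from the same database.

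**The retests are not lost.** This stands. A reader might infer that they drop out of the liver safety evaluation altogether, and the documents do not support that. Listings are provided for participants with abnormal results (SAP 15.2.5). Aminotransferase and bilirubin increases are AESIs, tabulated by preferred term (SAP 15.2.3), and ALT and AST increases are Tier 1 events (SAP 15.1.2). The hold criteria in Protocol 4.1 are not restricted to scheduled visits.

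**A percentage cannot be justified.** This also stands. It is tempting to say that a bilirubin rise lasting d days is seen at a weekly visit with probability d/7 (2/7 = 29% for 2 days). The documents give no duration, retests follow a trigger and are not randomly timed, and Days 1 to 4 are sampled daily. Moreover, 1 − d/7 is not the share measured but left out, since a retest must also have caught the rise.

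**Using all post-dose values brings its own problem.** Values taken after rescue antimalarials would enter, possibly unequally across cohorts, while the protocol's TEAE definition (Section 9.4.2) stops before rescue. The fix below allows for this.

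**Conclusion.** The point holds for the laboratory-based liver displays. Applied as written, SAP 9.3 and 9.4 would leave nearly all Appendix 6 retests triggered from Day 8 onward out of the eDISH and ULN line plots. A later aminotransferase peak, or a bilirubin above 2 x ULN first seen at a retest, could then be missing from the Hy's Law display. The effect on shift tables is small and mainly concerns bilirubin.

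This rests on three assumptions: that the general rule governs figures for which 15.2.5 is silent, that the trigger arises at a scheduled visit, and that 48 to 72 hours means 2 or 3 calendar days. The number of participants affected cannot be derived.

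A reader might also infer that liver injury is the trial's main known harm. The visible text does not say so: liver and CNS events stand side by side as AESIs and hold criteria, and the risk section is redacted. The study is exploratory and descriptive and the values remain in the database, so this is a correctable specification fault, best settled before the outputs are programmed.

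**What to change.** In SAP 15.2.5:
- State that the eDISH plot and ULN line plots, and a worst-post-baseline shift table if one is produced, use all valid post-dose values, including repeat and unscheduled samples and those taken after an early EOS.
- Define peak ALT/AST and peak total bilirubin per participant, and how the two are related in time.
- Flag values taken after rescue antimalarial treatment, so that cohorts can be shown with and without them.

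Add a cross-reference in SAP 9.3 and keep its scheduled-only rule for by-visit summaries.

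The cost is a short addition to the SAP and a programming flag. No new data and no change to clinical procedures are needed.
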